1.1 Background and rationale

1.1.1 Magnitude of problem:

Obstructive sleep apnea (OSA) is caused by the cyclical upper airway collapses during sleep resulting in arousals, sleep fragmentation, intermittent oxygen desaturation, and sympathetic activation [1]. The prevalence of OSA in general population varied from approximately 2% to 26% worldwide [2, 3]. Prevalence of OSA in general population approximates 4% in men, and 2% in women [2]. Similarly, the prevalence of OSA in Thai population approximates 4.3-4.4% (5.3-15% male; 1.9-3.9% female) [4, 5]. However, it has been estimated that up to 93% of women and 82% of men with moderate to severe OSA have still remained undiagnosed [6]. The prevalence of sleep disordered breathing (SDB) in high-risk pregnancy was also high, which ranged from 20% to 35% (16-21) as for diagnosis based on objective sleep tests (e.g., polysomnography (PSG) or Watch-PAT) [7-12]. Recent meta-analysis showed the pooled prevalence of SDB during pregnancy of 26.7% (95%CI: 16.9%, 34.4%, $I^2=83.15%$) [13]. However, prevalence of SDB in pregnancy remains uncertain depending on various factors such as population studied (high vs low risk), type of diagnostic measures, and trimester of study.

1.1.2 Disease burden and impacts

Growing evidences indicated that sleep disordered breathing during pregnancy is associated with poor maternal and fetal outcomes, e.g., gestational hypertension (GHT), pre-eclampsia, gestational diabetes (GDM) and low infant birth weight as for evidences from meta-analyses [14-16]. This might be due to physiologic and hormonal changes in pregnancy and thus predispose towards development of new-onset or exacerbation of SDB [17].

However, diagnosis and screening of SDB during pregnancy are challenging. Although in-laboratory PSG is the gold standard diagnostic test, long waiting periods for appointments, particularly considering the short time-window to perform the test early during the pregnancy, and the discomfort induced by the sleep test may lead to absence of investigation [18, 19].

Thus, simple and accurate screening strategies should be investigated. Risk stratification for the probability of OSA in pregnant women will also help in prioritizing the need for further diagnostic sleep testing given the limited resources in many places throughout the world. Early diagnosis and treatment of OSA in pregnancy should be implemented given the potential benefit on pregnancy outcomes [20, 21].

Our recent systematic review and meta-analysis showed that conventional OSA screening questionnaire such as the Berlin questionnaire and Epworth sleepiness scale had poor performance during pregnancy. We conclude that the poor discriminative values might be related to the facts that 1) both OSA and pregnancy lead to similar sleep complaints; 2) that there is a continuous change in symptomatology and the severity of the sleep-disordered-breathing with progression of pregnancy; 3) that the standard and threshold to diagnose SDB during pregnancy has not been defined; 4) finally that the timing of the questionnaire administration is not standardized.

And there is a need for screening tool that take into account the change overtime of the symptoms of OSA, and pregnancy. New screening tools and strategies specific to pregnancy that enable us to sequentially screen and monitor for OSA throughout pregnancy should be developed.

1.1.3 Treatment & goal of treatments

Nasal continuous positive airway pressure (CPAP), the standard treatment for OSA in non-pregnant population. CPAP has been shown to reduce cardiovascular mortality, morbidity, and blood pressure [22-25]. However, there are limited data regarding the efficacy of CPAP treatment in pregnancy. CPAP also has been proposed as the adjunct therapy for pre-eclampsia [26]. Despite the safety use of CPAP in pregnant women, the results regarding improvement of pregnancy outcome were lacking [27]. Extrapolation of treatment effect of CPAP from other population may not apply to pregnancy given a different physiology during pregnancy and the effect on the fetus.

We performed a systematic review in search of the existing studies concerning the efficacy of CPAP treatment for SDB during pregnancy. Of the 7 studies included (n=111), only 3 studies were randomized controlled trials (RCT), and the other 4 studies were experimental studies with pre-post design. And of the 3 RCTs, only 1 study initiated CPAP during 1st trimester and throughout pregnancy, the other 2 RCTs applied CPAP for only 1 night.

Significant results for CPAP efficacy regarding BP-lowering effects were reported in 2 studies with the early pregnancy and long-term use, and 2 studies with 1-night use of CPAP in the pre-eclamptic women during 3rd trimester, while 1 study in gestational hypertension women with 1-night use of CPAP showed no treatment effect.

Data on pregnancy outcomes were reported in the 3 long-term early CPAP use studies. While CPAP use seemed to prevent the incidence of preeclampsia, and preterm in pregnant women with chronic HT, this was not the case in women with preeclampsia risk and obesity.

Based on the rarity of evidence, it is too early to make any conclusion given the limitation in the sample size of the studies, the difference in study design, outcome measurement, the timing and duration of CPAP administration, and characters of subjects included. However, there are some important conclusions that we can make. First, despite the association of SDB and poor maternal and fetal outcomes shown in meta-analyses, there is not enough evidence from existing studies that CPAP treatment can improve pregnancy outcomes particularly, the reduction of preeclampsia and preterm labor. Second, there is no definite cut-off threshold for SDB diagnosis during pregnancy. Third, early and long-term CPAP treatment initiating during 1st trimester seemed more promising than in late pregnancy in improvement of pregnancy outcome. And lastly, in pre-eclamptic women during late pregnancy there is no evidence that CPAP can modify the disease progression, although 1-night CPAP might lower nocturnal blood pressure.

Hence, SDB pose a significant threat to pregnancy and fetus, diagnosis and treatment of SDB during pregnancy are still challenging given the dynamic changes of pregnancy and SDB. Because of the lack of evidence for the diagnostic and treatment threshold for SDB during pregnancy, there is currently no standard guideline to systematically screen and treat for SDB during pregnancy. The situation of SDB during pregnancy is in state of “clinical equipoise”, where the scientific community needs a strong evidence to make any treatment recommendation for the care of pregnant women at risk. It is an urgent need to conduct a randomized controlled trial that can demonstrate the efficacy of CPAP treatment in high risk pregnant women.

1.2 Research Question

1.2.1 Does the use of CPAP treatment for SDB in pregnant women with preeclampsia risk result in better blood pressure control and thus reduce related maternal and fetal complications than standard usual antenatal care in control group

1.2.2 We want to investigate whether our proposed screening algorithm for SDB specific to pregnancy is accurate and feasible in monitoring and diagnosis of SDB during pregnancy.

1.3 Research Objectives

1.3.1 **Primary Objective:** To compare whether the treatment effect of CPAP on SDB during pregnancy can improve blood pressure control in high risk pregnancy

- Systolic/diastolic blood pressure during daytime ANC at 10:00-12:00 am at randomization (GA 0-16 week), 1.5-2 month after randomization (GA 18-20 week), and 3-4 month after randomization (GA 24-28 week), 5-6 month after randomization (GA 32-34 week) and monthly (GA>35 week) until delivery

1.3.2 **Secondary Objective:**

- To compare the composite outcome of pre-eclampsia/GHT, GDM, fetal growth restriction, and pre-term labor between the CPAP treatment and control groups. And individual outcomes.
- To compare the night-time blood pressure compared to control group. 2nd outcome

2.1 Definitions

Obstructive sleep apnea (OSA)/Sleep disordered breathing (SDB)/Upper airway resistance syndrome (UARS): Diagnostic criteria according to the International Classification of Sleep Disorders. 3rd Edition includes (A and B) or C satisfy the criteria [28]

A. The presence of 1 or more of the following:

1. The patients complain of sleepiness, nonrestorative sleep, fatigue, or insomnia symptom
2. The patient wakes with breath holding, gasping, or choking
3. The bed partner or other observer reports habitual snoring, breathing interruptions, or both during the patient's sleep.
4. The patient has been diagnosed with hypertension, a mood disorder, cognitive dysfunction, coronary artery disease, stroke, congestive heart failure, atrial fibrillation, or type 2 diabetes mellitus

B. PSG or out-of-center sleep test (OCST) demonstrates:

1. 5 or more predominantly obstructive respiratory events (obstructive and mixed apneas, hypopneas, or respiratory effort related arousal (RERAs) per hour of sleep during a PSG or per hour of monitoring (OSCT).

OR

C. PSG or OCST demonstrates:

1. 15 or more predominantly obstructive respiratory events (obstructive and mixed apneas, hypopneas, or respiratory effort related arousal (RERAs) per hour of sleep during a PSG or per hour of monitoring (OSCT).

Apnea: a reduction of thermistor signal at least 90% from baseline lasting for at least 10 seconds. Obstructive apnea is classified by the presence of RIP effort, and central apnea is classified by the absence of RIP effort [18].

Hypopnea: a reduction in nasal pressure transducer signal at least 30% from baseline that is associated with either O₂ desaturation $\geq 3\%$ from baseline or EEG arousal.

Respiratory effort related arousals (RERA): a sequence of breaths lasting ≥ 10 seconds characterized by increasing respiratory effort or by flattening of the inspiratory portion of the nasal pressure leading to arousal from sleep that does not meet the criteria for apnea or hypopnea.

Apnea-hypopnea index (AHI): = no. of apnea+hypopnea events/Total sleep time (hr)

Respiratory disturbance index (RDI): no. of apnea+hypopnea+RERA/Total sleep time (hr)

Hypertensive disorder of pregnancy consisted of 4 categories [29]

a) **Preeclampsia-eclampsia:** diagnostic criteria includes

▪ **Blood pressure:**

- $\geq 140/90$ mmHg on 2 occasions at least 4 hours apart after 20 weeks of gestation in a woman with a previously normal blood pressure
- $\geq 160/110$ mmHg, hypertension can be confirmed within a short interval (minutes) to facilitate timely antihypertensive therapy

And

▪ **Proteinuria**

- ≥ 300 mg per 24-hour urine collection (or this amount extrapolated from a timed collection) OR
- Protein/creatinine ratio ≥ 0.3 (each measured as mg/dL)
- Dipstick reading of 1+ (used only if other quantitative methods not available)

Or in the absence of proteinuria, new-onset hypertension with the new onset of any of the following:

- **Thrombocytopenia**
 - Platelet count $<100,000$ /microliter
 - **Renal insufficiency**
 - Serum creatinine concentration > 1.1 mg/dL or a doubling of the serum creatinine concentration in the absence of other renal disease
 - **Impaired liver function**
 - Elevated blood concentrations of liver transaminases to twice normal concentration
 - **Pulmonary edema**
 - **Cerebral or visual symptoms**
- b) Chronic hypertension (of any cause)** is hypertension that predates pregnancy
- c) Chronic hypertension with superimposed preeclampsia** is chronic hypertension in association with preeclampsia
- d) Gestational hypertension** is BP elevation after 20 weeks of gestation in the absence of proteinuria or the aforementioned systemic findings.

- **Two-step strategy**

- **Step 1:** perform 50-g GLT (nonfasting), with plasma glucose measurement at 1 h, at 24-28 weeks of gestation. If plasma glucose level at 1 hour after the load is 140 mg/dL, proceed to a 100-gm OGTT.
- **Step 2:** the 100-g OGTT should be performed when patient is fasting. The diagnosis of GDM is made if at least 2 of the following 4 plasma glucose levels are met or exceeded:

Carpenter/Coustan

- Fasting 95 mg/dL
- 1-hour 180 mg/dL
- 2-hour 155 mg/dL
- 3-hour 140 mg/dL

HbA1C, fasting plasma glucose, 1-hour plasma glucose, 2-hour plasma glucose had been shown to be predictor of preeclampsia.

Fetal growth restriction is defined as a customized birthweight <10th centile for gestational age [31].

Preterm labor is defined as is the [birth](#) of a [baby](#) at less than 37 weeks [gestational age](#) [31, 32]

2.2 Conceptual framework

Conceptual framework is shown in figure 1

3. METHODOLOGY

3.1 Study design and setting

The study design will be a multicenter randomized-controlled trial in 3 tertiary care hospitals including Ramathibodi Hospital, Phramongkutklao Hospital and Rajavithi Hospital.

3.1.1 Ramathibodi Hospital is a [university hospital](#) of the Faculty of Medicine Ramathibodi Hospital which is a faculty within [Mahidol University](#) and the fourth oldest medical school in Thailand. The hospital serves at least 5,000 out-patient visits per day and in-patients with more than 1,000 beds for tertiary medical care. The hospital provides approximately 3,000 antenatal care service and delivery each year. It will be the primary site of the research investigation. The study will initiate here in June 2016 and followed by other centers. The study will take approximately 2 years for the accrual time to achieve the target number of participants and another year for the completion and analysis.

3.1.2 Phramongkutklao College of Medicine is the first and only medical cadet school in [Thailand](#). The college is the seventh medical school established in Thailand by the will of [King Bhumibhol Adulyadej](#). Phramongkutklao College of Medicine is an affiliated college of [Mahidol University](#). It is the teaching hospital accommodating 1,200-bed in the tertiary level. The hospital provides approximately 3,000 antenatal care service and delivery each year. The research will start soon after the study initiation in Ramathibodi Hospital once the ethics committee and funding are approved. The study will take approximately 2 years for the accrual time to achieve the target number of participants and another year for the completion and analysis.

3.1.3 Rajavithi Hospital is a 1,200-bed medical center accommodating 40,000 in-patients and 1,000,000 out-patients yearly or a daily average of 4,000 patients, with 200,000 referral patients (both in and out patients). The hospital provides medical service at standard health promotion in tertiary levels and above, including quality referral system. The hospital provides approximately 4,000 antenatal care service and delivery each year. The research will start soon after the study initiation in Ramathibodi Hospital once the ethics committee and funding are approved. The study will take approximately 2 years for the accrual time to achieve the target number of participants and another year for the completion and analysis.

3.2 Study subjects

High risk pregnant women attending the antenatal care at the collaborated hospitals will be eligible for the study if they meet all following inclusion criteria.

3.2.1 Inclusion criteria (ALL criteria)

- Singleton pregnant women age ≥ 18 years without significant medical conditions such as immunocompromised status, chronic infection (HIV infection, tuberculosis), chronic lung and cardiac conditions, chronic kidney disease, thyroid disease, or neuromuscular disease.
- Pregnant women attending the 1st antenatal care and intending to deliver at one of the study hospitals with gestational age < 16 weeks
- Thai nationality with ability to use Thai language proficiently both in spoken and written language.
- Have been diagnosed as high-risk pregnancy by obstetricians by having any of the following conditions

- a. Chronic hypertension prior to pregnancy
- b. Hypertension during pregnancy before 20week gestation.
- c. Pre-eclampsia/gestational hypertension during recent pregnancy
- d. Obesity defined by pre-pregnancy body mass index (BMI) ≥ 27.5 kg/m²
- e. Having diabetes mellitus or history of gestational diabetes in previous pregnancy
- Having SDB by either definition
 - a) RDI ≥ 5 events/hour by sleep testing at either point of testing during early pregnancy (0-16 GA week) or late pregnancy (GA 24-28 week)
 - b) OR Presence of snoring (either as frequent snoring ≥ 3 times/week or loud snoring) prior to or occurring during pregnancy
- Sign written informed consent

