3.3 Randomization and allocation

A randomization list will be generated and stratified by trimesters. For each stratum, a block randomization with varying block size from 4 to 8.

Preparation of randomization will be done by a third party, not involved in the clinical trial. Randomization sequence codes were generated using centralized computer system. Once eligible participants had agreed to participate the study and signed informed consent, the investigators entered clinical details into the system. Then the computer system generated the automatic randomization sequence and immediately sent back to the investigators for further allocation accordingly. After randomization and allocation, participants in the CPAP intervention group received CPAP treatment nightly throughout pregnancy until delivery.

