3.7.2 Control Group

- Subjects will receive standard antenatal care and follow-up plan similar to the intervention group.

Primary outcome

- Systolic and diastolic blood pressure, which will be measured at rest using sphygmomanometer twice on both arms by research nurses during daytime ANC at 10:00-12:00 pm at randomization (GA 0-16 week), 1.5-2 month after randomization (GA 18-20 week), and 3-4 month after randomization (GA 24-28 week), 5-6 month after randomization (GA 32-34 week) and monthly (GA>35 week) until delivery

Secondary outcome

- 24-hour ambulatory blood pressure monitoring (daytime versus night time) using the non-invasive technique from pulse transit time (SomnoTouch NIBP).
- Pregnancy complication listed as composite endpoints below

(Composite endpoint): A combination of clinical endpoints in maternal and fetal outcomes, data from Ramathibodi hospital during 2013-2014) *

- **Composite 1:** hypertensive disorder of pregnancy;
- **Composite 2:** hypertensive disorder of pregnancy or preterm labor or fetal growth restriction
- **Composite 3:** Preterm labor or fetal growth restriction, or severe pre-eclampsia or eclampsia or death; (composite 3 incidence=10%)

*Given that the incidence of hypertensive disorder incidence= $136/3787=3.6\%$;
gestational diabetes incidence= $601/3787=15.9\%$; fetal growth restriction incidence= $157/3787=4.1\%$; preterm labor incidence=10%; and severe pre-eclampsia/eclampsia/HELLP syndrome incidence= $(43+ 1+3=46/3787=1.2\%)$, respectively.

- Individual component of the composite endpoints including incidence of hypertensive disorder of pregnancy, gestational diabetes, preterm labor, and fetal growth restriction
- Glucose level, Oral Glucose Tolerance Test (OGTT), HbA1C
- Fetal ultrasound results: uterine Doppler arterial blood flow, fetal growth restriction
- Neonatal outcome: birth-weight, APGAR score, Length of stay, NICU admission

- Placenta character: weight will be measured at birth by the neonatal nurse.

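### Eligibility allows a qualifying sleep test at GA 24-28 weeks, but the primary outcome fixes randomisation at GA 0-16; if anyone enters late, untreated readings could be counted as outcomes

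*Protocol*

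**What the plan says.** Section 3.2.1 (same text in both documents) requires all inclusion criteria to be met. One is first antenatal attendance, with the woman "intending to deliver at one of the study hospitals with gestational age < 16 weeks". Another is sleep-disordered breathing, which can be met by an RDI of at least 5 "events/hour by sleep testing at either point of testing during early pregnancy (0-16 GA week) or late pregnancy (GA 24-28 week". The alternative route has no test date: "OR Presence of snoring (either as frequent snoring ≥ 3 times/week or loud snoring) prior to or occurring during pregnancy".

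The primary outcome (Protocol 3.7.2; Combined document, Primary outcome; also 1.3.1 in both) is clinic blood pressure "at randomization (GA 0-16 week), 1.5-2 month after randomization (GA 18-20 week), and 3-4 month after randomization (GA 24-28 week", then "5-6 month after randomization (GA 32-34 week", then monthly after GA 35. The three follow-up visits before GA 35 therefore each carry two time labels.

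The flow chart in both documents marks the sleep study at enrolment only. Section 3.7.1 starts CPAP straight after allocation. Section 3.10.4 tests the change in diastolic pressure with a t-test; it names no visit, does not define baseline, and has no rule for readings or events before randomisation. Protocol 3.3 has the list "stratified by trimesters"; section 3.3 of the Combined document stratifies by centre.

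**The concern.** A sleep test at GA 24-28 weeks can serve as an entry criterion only if entry can follow it. The outcome schedule has no place for a woman who enters then. If one is randomised, someone must decide which of her readings is baseline and which are follow-up, and section 3.10.4 gives no rule.

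The outcome side matters most. A GA 18-20 reading in a woman randomised at 24-28 weeks was taken before either arm began, so its expected treatment difference is zero. Counting it as follow-up dilutes the estimate. The same applies to hypertensive disorders, which section 2.1 diagnoses after 20 weeks and which enter the composites: an event between week 20 and a late randomisation cannot be a consequence of allocation. Using a GA 0-16 reading as baseline for a late entrant is less serious. It is still a pre-randomisation value, so it costs precision and does not itself bias the comparison.

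**Working it through.** **1. The plan's own sample size.** Inputs from section 3.9.1: difference 2.5 mmHg, SD 7.4, two-sided alpha 0.05, power 0.80, ratio 1:1.

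n per arm = 2 × (1.960 + 0.842)² × 7.4² / 2.5² = 137.5, so 138 by the normal approximation. The t-based calculation gives 139 per arm, 278 in total, which is the plan's figure.

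**2. Length of a month.** The documents call the first follow-up both 1.5-2 months (primary outcome) and 6-8 weeks (section 3.10.4 and the flow chart), which implies 4 weeks per month. A calendar month is about 4.35 weeks. Both are used below.

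**3. A woman randomised at GA 24-28.** The lower limit is 24 plus the short end of the month window; the upper limit is 28 plus the long end.

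| Visit label | GA label | GA at 4 wk/month | GA at 4.35 wk/month |
|---|---|---|---|
| 1.5-2 months | 18-20 | 30-36 | 30.5-36.7 |
| 3-4 months | 24-28 | 36-44 | 37.0-45.4 |
| 5-6 months | 32-34 | 44-52 | 45.7-54.1 |

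No row agrees with its GA label. Going by GA instead, the 18-20 week reading precedes randomisation by between 24 − 20 = 4 and 28 − 18 = 10 weeks, and the 24-28 week reading can at best coincide with randomisation.

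**4. Early entrants.** The two windows for a visit overlap if GA at randomisation lies between (lower GA limit − longest interval) and (upper GA limit − shortest interval).

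| Visit | 4 wk/month | 4.35 wk/month |
|---|---|---|
| GA 18-20 | 10 to 14 | 9.3 to 13.5 |
| GA 24-28 | 8 to 16 | 6.6 to 15.0 |
| GA 32-34 | 8 to 14 | 5.9 to 12.3 |
| All three | 10 to 14 | 9.3 to 12.3 |

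So both labels can hold at every visit only for randomisation at about GA 9-14, allowing either convention. At 15.9 weeks, which the entry rule permits, 1.5-2 months later is GA 21.9-23.9 (4 weeks) or 22.4-24.6 (4.35 weeks), not 18-20.

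**5. Illustration of dilution.** Let f be the share of analysed values taken before randomisation, with no effect in them and the SD unchanged. The documents give no value for f; the values below are assumptions. The expected difference is 2.5 × (1 − f). Two-sample t-test, 139 per arm, SD 7.4:

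| f | Difference (mmHg) | Power |
|---|---|---|
| 0 | 2.50 | 0.80 |
| 10% | 2.25 | 0.71 |
| 20% | 2.00 | 0.61 |
| 30% | 1.75 | 0.50 |

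The normal approximation differs by no more than 0.01 (0.80, 0.72, 0.62, 0.50).

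**The case against.** Much of the text points to early randomisation only. The primary outcome puts randomisation at GA 0-16. The flow chart has one sleep study, at enrolment, and calls the visit 6 to 8 weeks later second trimester. Section 3.7.1 treats 24-28 weeks as the time for a further pressure adjustment, which presupposes that CPAP has already begun. The snoring route admits many women early, so a late qualifier would need neither early snoring nor an early RDI of 5. On this reading the 24-28 week clause is residual text and no late entrants arise. Moreover, each follow-up visit before GA 35 is described as after randomisation, so an analyst who respects that label would not use an earlier reading.

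This stands as far as it goes: the harm requires both that late randomisation happens and that visits are assigned by GA window.

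A reader might infer from "stratified by trimesters" that late randomisation was intended. The documents do not establish that. Entry before 16 weeks already spans the late first and early second trimester, so trimester strata fit early entry too. The Combined document carries the same 24-28 week clause with strata by centre.

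A reader might also conclude that the two visit labels disagree for most women. No distribution of GA at entry is given, and the labels are approximate. Only the range in which they agree can be stated.

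**Conclusion.** The contradiction is certain; its effect is conditional. Eligibility, the sleep-test schedule and the outcome schedule cannot all hold for a woman who first qualifies at GA 24-28, and the analysis section has no rule that would settle her case. If such women are randomised and visits are assigned by GA window, untreated readings and events from before randomisation count as outcomes, and the bias is toward no difference. If nobody is randomised after 16 weeks, that problem disappears. What then remains is an entry clause with no function and a pair of visit labels that agree throughout only for entry at about GA 9-14.

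The size is unknown. It would be tempting to report that power falls to 0.61, but the documents do not support that as an estimate: the share of late entrants is assumed, and section 3.10.4 does not name the 18-20 week visit, or any other, as the one analysed. The power figures show only what dilution would cost at given shares.

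The point is worth acting on because the remedy is cheap and removes the ambiguity under either reading.

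**What to change.** - Reconcile 3.2.1, 3.3, 3.7.2 and the flow chart on when randomisation may occur and which sleep test can qualify a woman. State which stratification factor was used, since the two documents differ; this may be only a change between versions.
- Define baseline as the last blood pressure reading at or before randomisation.
- Count only readings and events after randomisation as outcomes. State how hypertensive disorders already present at randomisation are handled.
- Name the primary visit and give it one clock. Either is defensible: by gestational age, women entering at 8 and 15 weeks are compared at the same GA with 7 weeks' difference in time since randomisation; by time since randomisation, the reverse. Randomisation balances both between arms, so what matters is that the choice is written down.
- Replace the unadjusted t-test with a model that includes the stratification factor actually used (trimester in the Protocol).

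The cost is protocol and SAP wording and slightly more analysis work. No new data are needed if visit and randomisation dates are held: the last menstrual period is collected (3.6.1.1), so gestational age at each reading can be derived.
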